6.14.3.8. Hypersensitivity Reactions

Two main analyses are performed in support of assessment of potential immediate hypersensitivity, including anaphylaxis as well as potential nonimmediate hypersensitivity.

Time Period A, of potential immediate hypersensitivity includes all TEAEs occurring from start of study drug administration up to 24 hours after end of study drug administration. For events without the hypersensitivity electronic case report form (eCRF), only date (no time) information are collected, the event occurred on the same date as the study drug injection date will be included in Time Period A.

Time Period B, of potential non-immediate hypersensitivity, includes all TEAEs occurring more than 24 hours after the end of study drug administration, but prior to subsequent drug administration.

The counts and percentages of participants who experienced a TEAE will be summarized by PT with decreasing frequency by treatment.

Detailed searching criteria can be found in [Appendix 3](#). Within query, individual PTs that satisfied the queries will be summarized. For Time Period A analysis, the Anaphylactic reaction SMQ algorithm will be summarized. Also, a single event may satisfy multiple SMQs, in which case the event contributes to every applicable SMQ.

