10.3.1.7. Hypersensitivity Events

All allergic or hypersensitivity reactions will be reported by the investigator as either AEs, or if any serious criterion is met, as SAEs.

In the event of suspected drug hypersensitivity reactions (immediate or nonimmediate) in subjects who experience moderate-to-severe injection reactions as assessed by the investigator, unscheduled blood samples will be collected for PK and ADA analyses at the following time points:

- as close as possible to the onset of the event
- at the resolution of the event
- 30 (\pm 3) days following the event.

Additionally, unscheduled serum samples for immune safety laboratory testing (including, but not limited to β tryptase, total IgE, complement, and cytokine panel testing) should also be collected at approximately 60 to 120 minutes and 4 to 6 weeks after the onset of the event in these participants.

Additional data, such as type of reaction and treatment received, will be collected on any AEs or SAEs that the investigator deems related to study drug(s) via the eCRF created for this purpose. Study drug(s) should be temporarily interrupted in any individual suspected of having a severe or serious allergic reaction to study drug(s). Study drug(s) may be restarted when/if it is safe to do so, in the opinion of the investigator.

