For the Anaphylactic reaction SMQ, each term is classified by scope (Narrow, Broad) and by category (A, B, C, D). All Narrow terms are category A, and all Broad terms are category B, C, or D. In addition to the usual Narrow and Broad searches, the SMQ defines an algorithm to further refine the cases of interest. For Time Period A analysis, the Anaphylactic reaction SMQ algorithm will be included. The algorithm is based upon events that occur within Time Period A. The counts and percentages of participants who experienced a TEAE for the following will be analyzed for each of the 2 time periods:

- any narrow term from any one of the 4 SMQs indicated above (that is, combined search across narrow of all 4 SMQs)
- any narrow scope term within each SMQ, separately (that is, narrow SMQ search). For Time Period A analysis, any term from Anaphylactic reaction SMQ algorithm.

Injection Site Reactions

The ISR AE will be identified using the MedDRA PT in any of the following:

- HLT of Injection site reaction
- HLT of Administration site reaction
- HLT of Infusion Site Reactions

Pancreatitis Events

Determination of investigator-reported events will be through the “Acute pancreatitis” MedDRA SMQ (20000022, narrow scope) and a “Chronic pancreatitis” PT search of the AE database, while adjudication-confirmed pancreatitis are found from adjudication forms.

Malignancy

The malignancy events will be identified using the MedDRA PT contained in Malignant tumours SMQ (20000194) narrow scope or Tumours of unspecified malignancy SMQ (20000195) narrow scope.

Major Depressive Disorder/Suicidal Ideation

AEs will be searched using MedDRA PTs from SMQs narrow scope: 20000037 [Suicide/self-injury] and 20000167 [Depression (excl suicide and self injury)].

Metabolic Acidosis, Including Diabetic Ketoacidosis

Metabolic acidosis including diabetic ketoacidosis will be identified using the following MedDRA PTs:

- Diabetic ketoacidosis
- Ketoacidosis
- Euglycaemic diabetic ketoacidosis
- Ketonuria
- Diabetic ketosis
- Diabetic ketoacidotic hyperglycaemic coma
- Ketosis
- Lactic acidosis
- Urine ketone body present
- Blood ketone body
- Blood ketone body increased
- Urine ketone body, and
- Blood ketone body present.

Supraventricular Arrhythmias and Cardiac Conduction Disorders

The supraventricular arrhythmias and cardiac conduction disorders events will be identified using the MedDRA PT contained in any of the following SMQs:

- 1) Supraventricular Arrhythmias:

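### SAP 6.14.3.8 has no rule for date-only hypersensitivity events on the day after injection, so some events within 24 hours drop out of Time Period A and the anaphylaxis algorithm

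*SAP*

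**What the plan says.** SAP 6.14.3.8 splits hypersensitivity events by time since injection. Time Period A "includes all TEAEs occurring from start of study drug administration up to 24 hours after end of study drug administration". Time Period B "includes all TEAEs occurring more than 24 hours after the end of study drug administration, but prior to subsequent drug administration".

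Both definitions need a clock time. The SAP recognises that some events lack one: "For events without the hypersensitivity electronic case report form (eCRF), only date (no time) information are collected". For these its whole instruction is that "the event occurred on the same date as the study drug injection date will be included in Time Period A". It gives no rule for a date-only event on the following date, and Period B has no date-only rule.

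SAP Appendix 3 applies the Anaphylactic reaction SMQ algorithm in the Period A analysis and says: "The algorithm is based upon events that occur within Time Period A". The Narrow-term searches across the four SMQs, by contrast, "will be analyzed for each of the 2 time periods".

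Protocol 6.1 places no restriction on the time of day of the weekly injection and has participants record the date and time of each dose in the diary. Protocol 10.3.1.7 collects additional data, on a dedicated eCRF, for events the investigator judges related to study drug.

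**The concern.** For date-only events the calendar rule does not deliver the SAP's own 24-hour definition. After a 20:00 injection only 4 of the 24 hours fall on the injection date. An event 8 hours later begins at 04:00 on the next date, is immediate by definition, and is not admitted to Period A if only its date is known.

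The consequence is sharpest for the anaphylaxis algorithm. Appendix 3 says that all Narrow terms in that SMQ are category A and all Broad terms are category B, C or D, so a case that only the algorithm finds rests on Broad terms. The other hypersensitivity searches use Narrow terms. A Broad component outside Period A is therefore picked up elsewhere in these searches only if the same term is Narrow in one of the other three SMQs. Otherwise it remains only in the general adverse event tables. The algorithm is also a criterion in Table GPHK.6.10, so if it is computed there as in Appendix 3, the omission carries into the summary of events by antibody status.

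**Working it through.** The plan states no figure on this point, so there is nothing to reproduce. The check has a textual step and an illustrative calculation.

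**Where a next-date event goes.** Suppose a date-only event falls on the day after an injection at clock hour *t*. It lies somewhere between 24 − *t* and 48 − *t* hours after the dose. For any *t* strictly between 0 and 24 that interval contains the 24-hour mark, so the event may belong to either period. The same-date rule does not admit it to Period A. Period B requires more than 24 hours, which cannot be shown. The event goes to Period B by default or to neither; in both cases it is outside Period A and outside the algorithm.

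**Share of the 24-hour window left out.** Onsets between 24 − *t* and 24 hours after the dose fall on the next date.

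- Uniform onset over 24 hours: share = *t*/24.
- Exponential onset with mean *m* hours, truncated at 24 hours, with F(x) = 1 − exp(−x/*m*): share = [F(24) − F(24 − *t*)] / F(24).
- Averaged over clock times uniform on 0–24 hours: 1/2 for uniform onset, and 1 + *m*/24 − 1/F(24) for exponential onset.

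Inputs: the 24-hour limit is from SAP 6.14.3.8. The onset patterns and clock times are assumptions, because the documents give neither distribution.

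| Injection time | Mean 1 h | Mean 4 h | Mean 12 h | Uniform |
|---|---|---|---|---|
| 08:00 | 0% | 2% | 15% | 8/24 = 33% |
| 12:00 | 0% | 5% | 27% | 12/24 = 50% |
| 20:00 | 2% | 37% | 67% | 20/24 = 83% |
| Averaged over clock times | 4% | 16% | 34% | 50% |

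Worked entry, 20:00 and mean 4 h: (e^(−4/4) − e^(−24/4)) / (1 − e^(−24/4)) = (0.3679 − 0.0025) / 0.9975 = 0.366.

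Worked average, mean 4 h: 1 + 4/24 − 1/0.9975 = 0.164.

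These are shares of date-only events that truly began within 24 hours. The number of such events is not given.

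**The case against.** The best defence is that the gap touches little.

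- **Few events qualify.** Only events without the hypersensitivity eCRF are affected, and Protocol 10.3.1.7 calls for additional eCRF data on events judged drug-related. If that is the form the SAP means, suspected drug reactions are the ones most likely to have a time. This stands. Separately reported component symptoms not judged related may lack the form, but that is plausible rather than documented.
- **Most displays do not depend on the period.** Narrow terms are analysed in both periods. AESI status in SAP 6.14.3.8.1 rests on severity or seriousness, and all TEAEs and SAEs are tabulated elsewhere. This stands, with the reservation that a Narrow-term event assigned to neither period would appear in neither period's summary.
- **Immediate reactions tend to start early.** With rapid onset the share left out is small. This stands as a reason not to lead with the uniform-onset figures, though the documents do not settle the onset pattern.
- **The rule also errs inclusively.** A same-date event that began before that day's injection counts in Period A. True, but this does not restore the next-date events.
- **Including next-date events misclassifies others.** After an 08:00 dose the next date covers 16 to 40 hours, and 16 of those 24 hours lie beyond the limit. This is a fair reason for a paired display rather than outright replacement.

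A reader might go further and infer that the rule hides a drug signal. The documents do not support that: related events are directed to an eCRF, and nothing shows that the date-only remainder is mainly drug reactions. A reader might also infer that the SAP assigns next-date events to Period B and so inflates the non-immediate count. No such assignment is written; it follows only by elimination, and the events may fall in neither period.

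**Conclusion.** The gap is real and should be closed. Following the SAP as written, date-only events on the day after injection are left out of Period A and out of the anaphylaxis algorithm even when they began within 24 hours. This can under-count immediate reactions and miss algorithm cases that depend on Broad terms. No primary, key secondary or severe/serious AESI result depends on it.

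The size cannot be fixed from the documents, which give no injection-time distribution, no onset distribution and no count of date-only events. Averaged over clock times, the share left out runs from about 4% with a mean onset of 1 hour to 50% with uniform onset. It is near 0% for rapid reactions to morning doses and 83% for uniform onset after a 20:00 dose. The high figures rest on uniform onset and should not be read as expected values.

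The current handling is also less cautious than the SAP's treatment of similar gaps. In 6.14.1.1, first-dose-day events without timing information count as post-treatment, and a missing postbaseline severity is treated as severe when treatment-emergence is determined.

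**What to change.** In SAP 6.14.3.8 and the hypersensitivity part of Appendix 3:

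1. State where date-only events on the calendar date after an injection are assigned.
2. Present the Period A summaries and the Anaphylactic reaction SMQ algorithm with date-only events on the injection date or the next calendar date counted in Period A, beside the same-date version.

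The diary injection time does not replace this rule. With the injection time known, the next-date interval still straddles 24 hours, because the missing item is the time of the event.

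The cost is about a sentence in the SAP and some programming. The downside is that some events from 24 to just under 48 hours after a dose count as immediate in the inclusive display, and the algorithm may combine symptoms that far apart. Showing both versions makes the size of that effect visible.

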6.14.3.8.1. Severe/Serious Hypersensitivity Reactions

The serious/severe cases of treatment-emergent hypersensitivity will be considered as AESIs. All serious hypersensitivity events will be collected with the SAE form. A listing of participants with serious hypersensitivity reactions may be provided if deemed necessary.

6.14.3.9. Injection Site Reaction

Injection site reactions, incidence and rates, and related information reported via the “Injection Site Reactions” eCRF will be summarized by treatment. Information to be summarized includes the location of the reaction, timing of the reaction relative to study drug administration, and characteristics of the injection site reaction: erythema, induration, pain, pruritis, and edema.

Patient-based analysis and event-based analysis may be provided if necessary. The patient-based analysis summarizes all injection-site reaction (ISR) questionnaire forms for an individual patient with a single statistic, typically an extreme value. This analysis allows each patient to contribute only once for each parameter, at the expense of a focus on the most extreme events. By contrast, the event-based analysis summarizes all ISR questionnaire forms received, without regard to individual patients. This provides characteristics of ISR events as a proportion of all events for which questionnaire responses were provided, at the expense of some potential bias due to differential contribution of individual patients to the analysis.

The counts and percentages of participants with treatment emergent injection site reaction will be summarized by treatment using the MedDRA PTs. Detailed searching criteria can be found in [Appendix 3](#).

The PT will be listed for summary in decreasing order of incidence for tirzepatide-treated participants.

6.14.3.9.1. Severe/Serious Injection Site Reactions

The severe/serious treatment-emergent injection site reactions (for example, abscess, cellulitis, erythema, hematomas/hemorrhage, exfoliation/necrosis, pain, subcutaneous nodules, swelling, induration, inflammation) will be considered as AESIs.

The counts and percentage of participants with severe/serious treatment-emergent ISRs will be summarized by treatment. A listing of participants with treatment-emergent severe/serious ISRs may be provided, if deemed necessary.

6.14.3.10. Major Adverse Cardiovascular Events

The following positively adjudicated major adverse cardiovascular events (MACE) will be considered as AESIs:

- death due to cardiovascular AEs
- myocardial infarction (MI),
- hospitalization for unstable angina,
- hospitalization for heart failure,
- coronary interventions (such as coronary artery bypass graft or percutaneous coronary intervention),

- cerebrovascular events, including cerebrovascular accident (stroke) and transient ischemic attack.

The counts and percentages of participants with positively adjudicated MACE may be summarized by treatment.

In addition, MACE reported by investigator may also be summarized although a major adverse cardiovascular event reported by investigator is not considered as AESI.

A listing of participants reporting MACE events, either reported by investigator or identified by the clinical endpoint committee (CEC), may be provided.

6.14.3.11. Major Depressive Disorder/Suicidal Ideation or Behavior

The severe/serious treatment-emergent major depressive disorder/suicidal ideation or behavior will be captured as AESI. Adverse events will be searched using MedDRA PT terms. Detailed searching criteria can be found in [Appendix 3](#).

The counts and percentages of participants with TEAEs will be summarized by treatment group using MedDRA PT nested within SMQ. Events will be ordered by decreasing frequency in the total tirzepatide group nested within SMQ. A listing of participants with major depressive disorder/suicidal ideation or behavior may be provided if deemed necessary.

Additionally, suicidal ideation and behavior, and depression will be assessed by the investigator via spontaneously reported AEs and through the use of the Columbia-Suicide Severity Rating Scale (C-SSRS) and the Patient Health Questionnaire (PHQ-9).

6.14.3.11.1. Patient Health Questionnaire

Total scores for the PHQ-9 range from 0 to 27 with total scores categorized as

- none (not depressed): 0 through 4
- mild: 5 through 9
- moderate: 10 through 14
- moderately severe: 15 through 19, and
- severe: 20 through 27.

Shift tables will be provided showing the counts and percentages of participants within each baseline category (maximum value) versus each postbaseline category (maximum value) by treatment.

Additionally, the following 3 outcomes of interest will be compared between treatments (based on the maximum value during baseline and postbaseline):

- any increase in depression category (that is, worsening of depression): includes participants in the none, mild, moderate, or moderately severe category during baseline and with at least 1 postbaseline measurement

- increase from No or Mild Depression to Moderate, Moderately Severe or Severe Depression: includes participants in the none or mild depression category during baseline and with at least 1 postbaseline measurement; and
- increase from Mild or Moderate Depression to Moderately Severe or Severe Depression: includes participants in the mild or moderate depression category during baseline and with at least 1 postbaseline measurement

6.14.3.11.2. Suicidal Ideation and Behavior Solicited Through C-SSRS

Suicide-related thoughts and behaviors occurring during the entire study period, based on the C-SSRS, will be summarized by treatment group. In particular, for each of the following suicide-related events, the counts and percentages of participants with the event will be summarized by treatment group:

- died by suicide
- nonfatal suicide attempt
- interrupted attempt
- aborted attempt
- preparatory acts or behavior
- active suicidal ideation with specific plan and intent
- active suicidal ideation with some intent to act without specific plan
- active suicidal ideation with any methods (no plan) without intent to act
- nonspecific active suicidal thoughts
- wish to be dead, and
- non-suicidal, self-injurious behavior.

In addition, the counts and percentages of participants who experienced at least 1 of the composite measures will be presented. The participants with at least 1 post-baseline C-SSRS assessment are included. The composite measure is determined at each assessment by the “yes” or “no” responses in C-SSRS categories by the study participant:

- Category 1 – Wish to be Dead
- Category 2 – Non-specific Active Suicidal Thoughts
- Category 3 – Active Suicidal Ideation with Any Methods (Not Plan) without Intent to Act
- Category 4 – Active Suicidal Ideation with Some Intent to Act, without Specific Plan
- Category 5 – Active Suicidal Ideation with Specific Plan and Intent
- Category 6 – Preparatory Acts or Behavior
- Category 7 – Aborted Attempt
- Category 8 – Interrupted Attempt

- Category 9 – Actual Attempt (non-fatal), and
- Category 10 – Completed Suicide.

Composite endpoints of suicidal ideation and suicidal behavior based on the above categories are defined below:

- **Suicidal ideation:** A “yes” answer at any time during study to any 1 of the 5 suicidal ideation questions (Categories 1 through 5) on the C-SSRS.
- **Suicidal behavior:** A “yes” answer at any time during study to any 1 of the 5 suicidal behavior questions (Categories 6 through 10) on the C-SSRS.
- **Suicidal ideation or behavior:** A “yes” answer at any time during study to any 1 of the 10 suicidal ideation and behavior questions (Categories 1 through 10) on the C-SSRS.

A listing contains data for each participant with suicidal ideation, suicidal behavior, or non-suicidal self-injurious behavior during the study by treatment and visit. Data from all visits are displayed, regardless of a “yes” or “no” answer, for participants with any “yes” answer for suicidal ideation, suicidal behavior, or self-injurious behavior without suicidal intent.

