Visit*	1	2	3*	4	5	6	7	8	9	10	11	12	13	14	15	16	17	18	19	20	21	99*	ED*	801*
Week of Treatment	-2	-1	0	4	8	12	16	20	24	28	32	36	40	44	48	52	56	60	64	68	72	72		4 wks Post TxP
Allowable Deviation (days)*		±3	±3	±3	+7	±3	+7	±3	±3	±3	±3	+7	±3	±3	±3	±3	±3	±3	±3	±3	±7	±7		±3
Fasting Visit*	X	X	X	X	X	X	X	X	X			X			X			X			X	X	X	X
Telephone Visit										X	X		X	X		X	X		X	X				
2-hour oral glucose tolerance test (includes glucose, insulin, c-peptide at each timepoint)*		X																			X		X	
Chemistry panel (include Cr for eGFR calculation and glucose)*	X		X			X			X			X			X			X			X		X	X
Lipid panel	X		X						X												X		X	X
Fasting insulin						X			X			X			X			X			X		X	X
C-peptide						X			X			X			X			X			X		X	X
Free fatty acids	X		X						X												X		X	X
Urinary albumin/creatinine	X*								X												X		X	X
Cystatin-c	X*								X												X		X	X
Calcitonin	X*					X			X												X		X	X
Hematology	X*					X			X												X		X	X
HbA1c	X		X			X			X			X			X			X			X		X	X
Pancreatic amylase, lipase	X		X			X			X												X		X	X
Thyroid-stimulating hormone	X*																							
Immunogenicity (includes PK sample)*			X	X		X			X						X						X		X	X
TZP PK*					X		X					X												
Pharmacogenetic stored sample			X																					

Visit*	1	2	3*	4	5	6	7	8	9	10	11	12	13	14	15	16	17	18	19	20	21	99*	ED*	801*
Week of Treatment	-2	-1	0	4	8	12	16	20	24	28	32	36	40	44	48	52	56	60	64	68	72	72		4 wks Post TxP
Allowable Deviation (days)*		±3	±3	±3	+7	±3	+7	±3	±3	±3	±3	+7	±3	±3	±3	±3	±3	±3	±3	±3	±7	±7		±3
Fasting Visit*	X	X	X	X	X	X	X	X	X			X			X			X			X	X	X	X
Telephone Visit										X	X		X	X		X	X		X	X				
Nonpharmacogenetic stored sample			X			X			X						X						X		X	X
Mental Health Questionnaires																								
PHQ-9*	X		X			X			X			X			X			X			X	X	X	X
C-SSRS (Baseline/Screening Version)*	X																							
C-SSRS (Since Last Visit Version)*		X	X	X	X	X	X	X	X	X	X	X	X	X	X	X	X	X	X	X	X	X	X	X
Self-Harm Supplement Form*	X	X	X	X	X	X	X	X	X	X	X	X	X	X	X	X	X	X	X	X	X	X	X	X
Self-Harm Follow-up Form*	X	X	X	X	X	X	X	X	X	X	X	X	X	X	X	X	X	X	X	X	X	X	X	X
Patient Reported Outcomes																								
PGIS			X																			X	X	
SF-36, version 2, acute form			X																			X	X	
IWQOL-Lite CT			X																			X	X	
EQ-5D-5L			X																			X	X	

1.3.2. Schedule of Activities for additional 2-year treatment period for participants with prediabetes at randomization

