16. Have a history of significant active or unstable Major Depressive Disorder (MDD) or other severe psychiatric disorder (for example, schizophrenia, bipolar disorder, or other serious mood or anxiety disorder) within the last 2 years

Note: Patients with MDD or generalized anxiety disorder whose disease state is considered stable and expected to remain stable throughout the course of the study, in the opinion of the investigator, may be considered for inclusion if they are not on excluded medications

17. Have any lifetime history of a suicide attempt
18. Have a Patient Health Questionnaire-9 (PHQ-9) score of 15 or more at Visit 1 or 3, prior to randomization
19. On the C-SSRS at Visits 1, 2, or 3, prior to randomization:
 - a “yes” answer to either Question 4 (Active Suicidal Ideation with Some Intent to Act, Without Specific Plan)
or
 - a “yes” answer to Question 5 (Active Suicidal Ideation with Specific Plan and Intent) on the "Suicidal Ideation" portion of the C-SSRS
or
 - a “yes” answer to any of the suicide-related behaviors (Actual Attempt, Interrupted Attempt, Aborted Attempt, Preparatory Act or Behavior) on the "Suicidal Behavior" portion of the C-SSRS
and
 - the ideation or behavior occurred within the past month
20. Have uncontrolled hypertension (SBP above or equal to 160 mmHg and/or diastolic blood pressure above or equal to 100 mmHg)
21. Have any of the following cardiovascular conditions within 3 months prior to randomization: acute myocardial infarction (MI), cerebrovascular accident (stroke), unstable angina, or hospitalization due to congestive heart failure (CHF)
22. Have NYHA Functional Classification IV CHF
23. Have acute or chronic hepatitis, signs and symptoms of any other liver disease other than nonalcoholic fatty liver disease, or any of the following, as determined by the central laboratory during screening:
 - alanine aminotransferase (ALT) level $>3.0X$ the upper limit of normal (ULN) for the reference range
or
 - alkaline phosphatase (ALP) level $>1.5X$ the ULN for the reference range
or
 - total bilirubin (TBL) level $>1.2X$ the ULN for the reference range (except for cases of known Gilbert’s Syndrome)

Note: Participants with nonalcoholic fatty liver disease are eligible to participate in this trial if their ALT level is $\leq 3.0X$ the ULN for the reference range

24. Have a calcitonin level (at Visit 1) of:

- ≥ 20 ng/L at Visit 1, if eGFR ≥ 60 mL/min/1.73 m²
 - ≥ 35 ng/L at Visit 1, if eGFR < 60 mL/min/1.73 m²

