8.2.6. Depression, Suicidal Ideation, and Behavior Risk Monitoring

Overweight and obese patients are at increased risk for depression (Luppino et al. 2010). Depression can increase the risk for suicidal ideation and behavior. Therefore, study participants will be screened at trial entry and monitored during the study for depression, and suicidal ideation and behavior.

Participants should be monitored appropriately and observed closely for suicidal ideation and behavior or any other unusual changes in behavior, especially at the beginning and end of the course of treatment, or at the time of dose changes, either increases or decreases. Consideration should be given to discontinuing study medication in subjects who experience signs of suicidal ideation or behavior, following a risk assessment (Section 7.1).

Baseline and treatment emergent assessment of depression, suicidal ideation and behavior will be monitored during the study using the C-SSRS and PHQ-9 (Section 8.3.1.1).

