6.14. Safety Analyses

Unless specified otherwise, safety assessments will be based on the SS (Table GPHK.6.1). All events that occur between the first dose date of study drug and the end date of study participation will be included, regardless of the adherence to study drug.

The statistical assessment of homogeneity of the distribution of categorical safety responses between tirzepatide doses and placebo will be conducted using Fisher's exact test, unless specified otherwise.

For selected continuous safety parameters, the mean change from baseline differences vs. placebo will be assessed via a MMRM using REML. Data from scheduled visits will be utilized for this analysis. Unless specified otherwise, the model for the analysis during 72 weeks treatment period will include country/pooled country, sex, prediabetes status at randomization, treatment group, visit and treatment-by-visit interaction as fixed effects, and baseline value of the safety parameter as a covariate. For the analysis during the 176 weeks treatment period (or 193 weeks), only participants with prediabetes at randomization in the SS will be included, and the model will contain the terms of country/pooled country, sex, treatment group, visit and treatment-by-visit interaction as fixed effects, and baseline value of the safety parameter as a covariate. To model the covariance structure within participants, the unstructured covariance matrix will be used. If this model fails to converge, the covariance structures specified in Section 6.13.1.1 will be tested in order until met convergence. If the data does not warrant the MMRM model, then ANCOVA model will be conducted.

For selected safety parameters, time-to-first-event analysis via the Cox-proportional hazards model may be conducted. Participants without the event will be censored at the end of study participation. For participants experiencing the event, the "time-to-first-event" will be the time (in days) from first dose to first occurrence of the event.

Where necessary, the rate of events will be analyzed using a generalized linear mixed-effects model assuming the number of events follow a negative binomial distribution and with treatment as a fixed effect. The logarithm of days during the active treatment period will be adjusted as an offset to account for possible unequal treatment duration of follow-up between participants.

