Unless otherwise specified, all the analyses listed in this section will be conducted using SS in the following 2 postbaseline periods, respectively:

- up to 72 weeks treatment period plus the safety follow-up (Visit 801, if applicable) for all randomized participants, and
- up to 176 weeks treatment period plus the safety follow-up (Visit 801 or Visit 802) for participants with prediabetes at randomization.

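### The C-SSRS composites are never compared with baseline, so ideation that was present before the first dose and persists counts the same as new ideation, and the plan has no treatment-emergent C-SSRS outcome

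*SAP*

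**What the plan says.** **C-SSRS analysis (SAP 6.14.3.11.2).** The section opens: "Suicide-related thoughts and behaviors occurring during the entire study period, based on the C-SSRS, will be summarized by treatment group". The ideation composite is a yes "answer at any time during study to any 1 of the 5 suicidal ideation questions (Categories 1 through 5) on the C-SSRS". The behaviour composite (Categories 6 to 10) and the combined composite have the same form. On who is analysed it says: "The participants with at least 1 post-baseline C-SSRS assessment are included". It contains no shift table, no worsening outcome and no reference to the baseline C-SSRS.

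**General safety rules (SAP 6.14 and Table GPHK.6.1).** On counting: "All events that occur between the first dose date of study drug and the end date of study participation will be included". On period, unless otherwise specified: "all the analyses listed in this section will be conducted using SS in the following 2 postbaseline periods, respectively". The Safety Analysis Set holds treatment-period and follow-up data.

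**Baseline collection and entry.** The protocol's Schedule of Activities (1.3.1) places the C-SSRS at Visits 1, 2 and 3. The first dose is given at the end of Visit 3. Exclusion criterion 19 (protocol 5.2) covers a yes to Question 4 or 5, or to any behaviour item, on condition that "the ideation or behavior occurred within the past month". It does not cover Categories 1 to 3.

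**Stated intent and the parallel instrument.** Protocol 8.2.6 says: "Baseline and treatment emergent assessment of depression, suicidal ideation and behavior will be monitored during the study using the C-SSRS and PHQ-9". For the PHQ-9, SAP 6.14.3.11.1 plans baseline-to-postbaseline shift tables and three category-increase outcomes compared between treatments.

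**The concern.** A by-arm safety summary of suicidality should separate what appeared or worsened after treatment began from what participants already had. The C-SSRS section does not do this, although the data needed are collected and the neighbouring PHQ-9 section does it.

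No other planned comparison fills the gap. Protocol 8.3.1.1 says that only serious events elicited through the C-SSRS or PHQ-9 are recorded as adverse events, and that nonserious ones are analysed separately. New nonserious ideation found by the questionnaire therefore does not reach the treatment-emergent adverse event summary in SAP 6.14.3.11. The C-SSRS summary is the planned by-arm analysis of it. Suicidal behaviour and ideation is also a named adverse event of special interest (protocol 9.4.4.3).

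If persisting baseline ideation is mixed with new ideation, the same expected background is added to every arm. That pulls the risk ratio toward 1 and lowers the chance of seeing an imbalance in a rare event.

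**Working it through.** **Step 1: which answers enter the numerator?**

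- SAP 6.14 counts events from first dose, sets two postbaseline periods, and uses an analysis set without screening data. Section 6.14.3.11.2 sits beneath these rules.
- Elsewhere the SAP refers to the whole study in order to bring in off-drug follow-up, not screening (liver enzymes 6.14.3.5.2, vital signs 6.14.4, ECG 6.14.5). The vital-sign rule then also requires a change during the postbaseline period.
- Section 6.14.3.11.2 applies a postbaseline condition to the composite denominator but states none for the numerator. Table GPHK.6.2 defines baseline and postbaseline for adverse events, laboratory tests, vital signs and ECGs, but not for the C-SSRS.

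The better reading is therefore postbaseline only. The wording leaves room for a programmer to do otherwise.

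**Step 2: what remains on the postbaseline reading?** A participant with Category 1 to 3 ideation at Visits 1 to 3 can be randomised. If that participant answers yes again after the first dose, the composite records an event identical to that of someone with no earlier ideation. No planned C-SSRS summary separates the two.

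**Step 3: how large could the dilution be?** The plan states no C-SSRS event rate or power, so there is no figure to reproduce. Every rate below is an assumption.

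- *p* = proportion with new ideation, placebo *p*c and tirzepatide *p*t.
- *s* = proportion with baseline ideation; *r* = proportion of those who report it again after dosing. On the postbaseline reading the background is *b* = *s* × *r*. For example, *s* = 2% and *r* = 50% give *b* = 1%. If screening answers themselves counted, *b* would equal *s*, so for a given *s* that reading gives the upper bound.
- Observed proportion *q* = *b* + (1 − *b*)*p*. Risk difference = (1 − *b*)(*p*t − *p*c).
- Arm sizes: 600 placebo and 1,800 tirzepatide combined (protocol 9.2). Two-sided alpha 0.05, normal approximation. Pooling the doses is part of the illustration.

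Worked row, *b* = 2%, *p* = 1% versus 3%: placebo 0.02 + 0.98 × 0.01 = 2.98%; tirzepatide 0.02 + 0.98 × 0.03 = 4.94%; ratio 4.94/2.98 = 1.66; difference 1.96 points.

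| *b* | 1% vs 3%: difference (points) | ratio | power | 0.5% vs 2%: difference (points) | ratio | power |
|---|---|---|---|---|---|---|
| 0 | 2.00 | 3.00 | 0.84 | 1.50 | 4.00 | 0.78 |
| 0.5% | 1.99 | 2.33 | 0.74 | 1.49 | 2.50 | 0.62 |
| 1% | 1.98 | 1.99 | 0.65 | 1.48 | 1.99 | 0.51 |
| 2% | 1.96 | 1.66 | 0.53 | 1.47 | 1.59 | 0.38 |
| 5% | 1.90 | 1.32 | 0.33 | 1.43 | 1.26 | 0.22 |

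Exact Fisher power for 0.5% versus 2% is close to these values: 0.79, 0.51, 0.37 and 0.21 at *b* = 0, 1%, 2% and 5%.

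The risk difference hardly moves. The ratio and the power fall.

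**The case against.** The strongest case on the other side has five parts.

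1. **The general rules already exclude pre-dose answers.** This stands. A reader might infer from the open-ended time wording that a yes at screening is itself an on-study event. The documents do not support that: Section 6.14 and the analysis-set definition govern, and nothing in 6.14.3.11.2 says that it overrides them. What is left is a numerator that should state the limit its denominator already has.

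2. **After Visit 1 the form asks about the time since the last visit.** A postbaseline yes is therefore ideation reported for an on-study interval, and counting it is a legitimate incidence summary. This also stands, and is a reason to keep the existing counts. It does not provide a treatment-emergent outcome.

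3. **Entry criteria shrink the background.** Criterion 17 excludes any lifetime suicide attempt, criterion 16 significant active or unstable major depression or other severe psychiatric disorder within two years, and criterion 18 a PHQ-9 score of 15 or more. The behaviour composite is thus little affected and the 5% row is unlikely. Category 1 to 3 ideation is still allowed, and criterion 16 permits stable depression.

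4. **Protocol 8.2.6 is a monitoring statement that leaves analysis to the SAP.** That is fair as a reading of its force. It still names the C-SSRS and PHQ-9 together, and the SAP follows through only for the PHQ-9.

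5. **Other outputs exist.** There is a treatment-emergent adverse event summary and an all-visits listing for anyone with a yes. The listing lets a reader trace individuals but compares nothing, and the adverse event summary omits nonserious events elicited by the questionnaire.

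It would also be too strong to infer that the analysis hides a treatment difference. The absolute difference is nearly unchanged, so dilution is the accurate word. Nor does a baseline comparison rescue every case: at 0.5% versus 1.0%, power is only about 0.13 even with no baseline ideation counted.

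**Conclusion.** The point holds as a gap in the analysis with a cheap remedy. The C-SSRS composites have no baseline comparison, so persisting Category 1 to 3 ideation is not distinguished from new ideation, and no treatment-emergent C-SSRS outcome is planned. The numerator wording also needs to be aligned with the postbaseline defaults, although those defaults should already keep screening answers out.

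The size is unknown because the documents give neither the proportion with baseline ideation nor how often it is reported again. Under the assumed rates, a background of 0.5% to 2% would lower power from 0.84 to between 0.74 and 0.53 (1% versus 3%), or from 0.78 to between 0.62 and 0.38 (0.5% versus 2%). These figures assume the same background in each arm. Randomisation balances baseline ideation in expectation, but not how often it persists if treatment affects that.

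**What to change.** In SAP 6.14.3.11.2:

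1. Define all three composites on any postbaseline assessment, in place of the open-ended time wording, so that numerator and denominator agree with each other and with Section 6.14.
2. Add, by treatment, a shift table or treatment-emergent summary against the maximum category at Visits 1 to 3. Ideation is treatment-emergent if a postbaseline category is higher than the baseline maximum, or if there is any yes when none was recorded at baseline. Behaviour is treatment-emergent if any postbaseline Category 6 to 10 is recorded when none was recorded at Visits 1 to 3.
3. State which recall period of the Visit 1 form defines the baseline maximum. Criterion 19 adds its own one-month condition, which suggests that the form can also capture older ideation.
4. Keep the existing any-postbaseline counts alongside.

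The cost is SAP wording, one derivation and one extra table, all from data already scheduled. No visit, assessment or clinical rule changes.
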